## **5. Monitoring and Withdrawal**

### **5.1. Clinical Evaluations**

Standard safety assessments for this study will include history and physical examinations, and vital signs at baseline and at 24 hours. Clinical assessments of SAEs and AEs will be performed at all study visits, as well as during phone encounters.

### **5.2. Laboratory Evaluations**

Standard laboratory evaluations will include clinical chemistry panel including renal, hepatic panels and electrolytes, CBC with differential, cortisol levels and stored samples as described in Appendix B and Appendix C.

### **5.3. Follow-up**

Follow-up will consist of phone-calls within a window of  $7 \pm 3$  days to coordinate the tapering schedule of prednisone. All changes in prednisone doses and tapers will be appropriately documented with concurrent eosinophil counts as applicable. Blood for RNA analysis will be obtained at 1 week to assess medium term effects of GC administration. The blood draw will be performed at the subject's home institution (with sample sent to NIH in accordance with appropriate procedures), or may be performed at NIH if the subject lives locally.

Subjects will be asked to return 2-4 weeks after the completion of their GC taper for their final visit on this protocol.

## 5.4. Early Termination Visit

Subjects who withdraw from the study prematurely (see below) will continue to be followed on Protocol #94-I-0079.

## 5.5. Re-contact of Subjects after Study Termination

After study termination, subjects will be contacted yearly as part of the required study visits for Protocol #94-I-0079. In settings where subjects request to withdraw consent for Protocol #94-I-0079, they will be asked whether they would be willing to be re-contacted in the future.

## 5.6. Premature Withdrawal of a Subject

Subjects may be withdrawn for the following reasons:

1. Significant adverse events from GC therapy requiring withdrawal of subject and/or switching to alternate therapies
2. Determination of positive F/P gene status during steroid therapy that was previously unknown.  
NOTE: Most subjects referred to NIH with HES have known F/P gene status and are already on tyrosine kinase inhibitors if indicated. In extremely rare cases where gene status is unknown, GC therapy might be initiated while F/P gene status is being investigated as part of Protocol #94-I-0079. If a positive result were obtained, the subject would be withdrawn from the study and imatinib therapy would be recommended. Such subjects would be excluded from the analysis.
3. Complete non-response to GC's evidenced by lack of reduction of peripheral eosinophil count from baseline at the initial 30 mg dose or the increased 60 mg dose. Subjects will be switched to an alternative therapy either by their primary care physician or at the follow-up visit. Although subjects will be withdrawn from further steroid tapering, evidence of non-response will be included in the analysis.
4. AEC  $\leq 1500/\mu\text{L}$  on the day of steroid challenge.
5. Subject becomes pregnant (subjects who become pregnant after the first GC dose will be followed for safety on 94-I-0079).

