### 3.4. Procedures and Laboratory Testing

Subjects will receive a single dose of prednisone prescribed by the PI or designee to be taken by mouth at a dose of 1 mg/kg (rounded to the nearest 5 mg) between the hours of 7:30 and 9am on the day of study. Laboratory testing, including a baseline cortisol level, CBC with differential, and research specimens (see Appendix B) will be drawn prior to prednisone administration and at 2, 4 and 24 hours after prednisone administration. Investigators will be blinded to the 2-hour, 4-hour and 24-hour eosinophil counts (the results will not appear in the NIH Clinical Research Information System (CRIS), but will be available from the Clinical Pathology internal system for analysis once the trial is completed). All blood draws will be timed and will occur in outpatient phlebotomy, outpatient clinic or inpatient unit that is able to draw at specific times to prevent variability in draw times across the subject cohorts.

In normal subjects, prednisone is rapidly absorbed and metabolized with peak levels at 2-4 hours and a biologic half-life of 12-36 hours. Serum will be stored from blood drawn at the 4-hour time point for assessment of synthetic glucocorticoid levels, including prednisone and its metabolite prednisolone. Subjects may be asked to undergo further workup for causes of poor absorption by their home physician or at NIH if indicated.

After the 24-hour challenge, subjects will be started on a GC taper to determine the lowest dose of GC that is able to suppress signs and symptoms of HES and maintain the peripheral eosinophil count below 1000/ $\mu$ l. GC will be initiated at 30 mg in all subjects, and the taper will proceed according to an algorithm (Appendix E). GC will be tapered by 5 mg weekly until a dose of 15 mg is reached. The dose will then be tapered by 2.5 mg weekly until a dose of 5 mg is reached or the eosinophil count rises.

In some cases, an initial starting dose of 30 mg of prednisone will be insufficient to control eosinophilia. If AEC is  $>1000/\mu$ L 1 week after the initiation of GC, the GC dose will be increased to 60 mg and a taper initiated from this higher dose. A CBC with

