differential will be drawn after 2 days on this higher dose and if the AEC remains  $>1000/\mu\text{L}$ , the subject will be withdrawn and total GC dose used for the final analysis will be the weight-based challenge dose for that individual. If the subject is responsive at the higher dose, the subject will be kept at 60 mg for one week after which the GC dose will be tapered by 10 mg every week until a dose of 30 mg of prednisone is reached. If AEC is still suppressed and they are able to continue the taper, they will then taper according to the standard taper schedule outlined above and shown in Appendix E.

Weekly eosinophil counts will be obtained with the taper until the AEC rises above  $1000/\mu\text{L}$  or the subject experiences HES symptoms. HES symptoms will be defined by the investigator and will be based on data collected at the time of the baseline visit, as well as clinical experience in the treatment of HES. If either eosinophils rise or HES symptoms are present, prednisone will be increased to the previous dose, and a taper will be re-attempted. If the AEC increases after an attempted decrease in dose, the rate of the tapering schedule will be decreased to 2.5 mg/week from 5 mg/week. The taper will continue according to this schedule until 2 attempts to taper from a given dose fail or a dose of 5 mg of prednisone is reached. If a subject's AEC continues to climb despite a dose increase, at the discretion of the investigator the dose may be increased by a larger dose than outlined in Appendix E. Attempts to capture the true effective dose of glucocorticoid that controls counts and symptoms will be attempted; however if not practical due to time or side effect profile of prednisone, subjects will return for an end of study visit and be removed from the study. If a subject is unable to be tapered, their responsiveness, or lack thereof, will be captured at that dose. Depending on the dose and the clinical presentation they may be continued on prednisone however they will be withdrawn from the protocol at the dose at which they were no longer able to taper.

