### **3.5. Study Endpoints**

#### **3.5.1. Primary Endpoint**

The primary response variable is GC responsiveness, defined as the lowest dose of prednisone at which eosinophils remain  $<1000/\mu\text{l}$ , for at least two consecutive weekly blood draws, and at which symptoms are controlled as determined by the investigator; OR, dose of prednisone at which subject is unable to taper prednisone further without rebound of eosinophilia and/or symptoms after three attempts; OR, the challenge dose, if there is no drop in eosinophil counts within the first week of challenge or taper.

GC responsiveness in each individual will be assessed using the percent change in eosinophil count (eosinophil response rate [ERR]) from baseline to 4h (or 24h) post-steroid challenge.

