## **4.2. Subject Exclusion Criteria**

A subject will not be eligible to participate in the study if any of the following apply:

1. Receiving >10 mg prednisone or equivalent at the time of enrollment.
2. Receiving ≤10 mg of prednisone or equivalent but have not been on a fixed dose for at least 3 weeks (subjects on a current corticosteroid taper will be excluded)
3. AEC ≤1500/μl on the day of the steroid challenge
4. Use of immunomodulatory medications, (other than ≤10 mg/day prednisone) including but not limited to biologics, within the past 6 months
5. Pregnant at the time of screening.
6. Have a known mutation in the FIP1L1-PDGFR gene
7. Any condition that, in the opinion of the investigator, places the subject at undue risk by participating in the protocol
8. Weight less than 48 kg (106 lbs) in subjects less than 18 years of age

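### Sections 3.4, 3.5.1 and 5.6 give conflicting paths, and possibly two endpoint values, to a subject whose eosinophils have not fallen after a week at 30 mg

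*Combined protocol and SAP*

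**What the plan says.** Section 3.4 starts every subject on 30 mg after the challenge. If AEC is above 1000/µL "1 week after the initiation of GC, the GC dose will be increased to 60 mg and a taper initiated from this higher dose". A further count is taken after two days at 60 mg. If AEC is still above 1000/µL, "the subject will be withdrawn and total GC dose used for the final analysis will be the weight-based challenge dose for that individual".

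Section 5.6 opens its list with "Subjects may be withdrawn for the following reasons". Item 3 is complete non-response, shown by a "lack of reduction of peripheral eosinophil count from baseline at the initial 30 mg dose or the increased 60 mg dose". The item then says that these subjects will be moved to another therapy, and adds: "Although subjects will be withdrawn from further steroid tapering, evidence of non-response will be included in the analysis".

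Section 3.5.1 defines the primary endpoint by three alternatives joined by OR, with no order among them:

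- Limb 1: the lowest dose that holds AEC below 1000/µL on two consecutive weekly draws "and at which symptoms are controlled as determined by the investigator".
- Limb 2: the dose that cannot be reduced without rebound after repeated attempts.
- Limb 3: the challenge dose, where eosinophils do not drop in the first week of challenge or taper.

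On symptoms during the taper, section 3.4 says: "If either eosinophils rise or HES symptoms are present, prednisone will be increased to the previous dose, and a taper will be re-attempted". It also fixes responsiveness, or its absence, at the dose reached when a subject cannot be tapered, and it allows an individualized course where a longer spell at a higher dose is clinically indicated. The taper algorithm itself (Appendix E) is a figure that is not available in the text.

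**The concern.** A subject whose count has not fallen after a week at 30 mg falls under two rules. One sends the subject to 60 mg. The other allows the subject to be declared a complete non-responder and taken off the taper. The choice affects care, and it can affect the number entered as the primary outcome. Such subjects are few and sit at the high-dose end of the scale, where a single value weighs heavily on a rank correlation. They also make up the group that the secondary objective sets out to identify.

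A second, smaller question arises at the same step. The readable trigger for 60 mg looks only at AEC, whereas limb 1 of the endpoint also requires symptom control. It is not clear what value is recorded for a subject at 30 mg whose AEC is below 1000/µL but whose symptoms persist.

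**Working it through.** **1. The plan's own figure.** Section 6.2 states 79.5% power for a two-sided 0.05 Spearman test with n = 32 and true correlation 0.5, and a Pearson sample size of 29.

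- Spearman, 20,000 simulated bivariate normal data sets, t approximation: 79.9%.
- Pearson, Fisher z: ((1.960 + 0.842) / atanh(0.5))² + 3 = (2.802 / 0.549)² + 3 = 29.0.

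Both reproduce. The sample-size statement is not in question.

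**2. Do the two triggers overlap?** Section 4.2 excludes anyone with AEC of 1500/µL or less "on the day of the steroid challenge". Taking that day's count as the baseline, no reduction means AEC still above 1500/µL, hence above 1000/µL. So every subject who meets the 30 mg part of item 3 also meets the escalation rule in 3.4.

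**3. Which value is recorded?** Limb 3 is taken here to be judged on the week-1 count. The challenge dose is 1 mg/kg rounded to the nearest 5 mg: 50 mg at 48 kg, 70 mg at 70 kg, 80 mg at 80 kg. All exceed 41 mg and are resistant under section 6.1.

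| Path for a subject with no fall at 30 mg | Value |
|---|---|
| Withdrawn under 5.6 | Challenge dose (limb 3) |
| Escalated under 3.4, 60 mg fails | Challenge dose (3.4) |
| Escalated under 3.4, then controlled | Challenge dose (limb 3) **or** lowest controlling dose (limb 1) |

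In the last row the taper in 3.4 runs 60, 50, 40, 30, 25, 20, 15, 12.5, 10, 7.5, 5 mg. The values 60 and 50 are resistant, 40 to 20 are moderately responsive, and 12.5 to 5 are responsive. All three categories are therefore possible. The score is at risk only for a subject who shows no fall in a week at 30 mg but is then controlled on 60 mg.

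**4. How many subjects?** The documents give no count. Section 1.1 cites more than 85% complete or partial response at 1 month, so fewer than 15% non-responders. Since 0.15 × 30 = 4.5, that is at most 4 of 30. Since 0.15 × 40 = 6 and the share is strictly below 15%, it is at most 5 of 40. That figure describes response at 1 month, not an eosinophil fall at one week on 30 mg, so it is only a guide.

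**5. Illustration of sensitivity.** Assume that the *k* subjects of 32 with the highest required dose are recorded at another value. If they stay tied at the top, power remains about 80% for *k* = 1 or 2. If they are recorded at the median instead, it falls to 74% (*k* = 1) or 68% (*k* = 2). This supposes that the high value was the right one, which the documents do not settle.

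**6. AEC below 1000/µL with uncontrolled symptoms at 30 mg, not escalated.** Limb 1 fails because symptoms are not controlled. Limb 2 needs rebound on taper attempts, and none has been made. Limb 3 fails because eosinophils did drop. The taper rule returns the subject to a previous dose, but 30 mg is the first taper dose. The readable text that could supply a value is the statement in 3.4 that responsiveness is fixed at the dose reached. On one reading that gives 30 mg, the same as for a subject truly controlled there. The assurance in section 6.3 that the endpoint is defined for uncontrolled subjects speaks of eosinophil counts only.

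**The case against.** A reader might infer that a subject with no fall at 30 mg must be both escalated and withdrawn. The documents do not say that. The list in 5.6 is permissive, so the conflict is mandatory escalation against permitted withdrawal. The two sections could be read together, with 3.4 applied first and 5.6 held in reserve. This is also a single-center study whose taper is coordinated by study telephone calls, so inconsistent practice between sites is not the issue. These points soften the conflict without resolving it: 3.4 leaves no discretion, 5.6 makes failure at 30 mg sufficient, and once non-response is called its consequences are mandatory.

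A reader might also infer that a symptomatic subject with AEC below 1000/µL has no route to a higher dose and is entered at 30 mg. That is not established. Section 3.4 allows an individualized higher-dose course with no AEC condition, the Appendix E algorithm cannot be seen, and the sentence on subjects who cannot be tapered covers absence of response as well as response. What stands is that 3.5.1 has no limb for this subject if the dose is not raised. Such a subject's count did fall, so the non-responder share in section 1.1 cannot be used to size this case.

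Finally, the primary objective is described as exploratory and the sample-size figure holds. Both weigh against treating this as critical.

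**Conclusion.** Wrong as written, at a severity below must-fix. Sections 3.4 and 5.6 conflict for every subject with no eosinophil fall after a week at 30 mg, given that challenge-day AEC is the baseline. The endpoint value is ambiguous for the subset later controlled on 60 mg: the challenge dose, or anything from 60 to 5 mg. Where 60 mg fails, both paths give the same score. The number affected is unknown. With at most 4 of 30 or 5 of 40 non-responders implied, one or two reassignments could matter to the resistant group and, on the illustration above, to the correlation test. The symptom case is a secondary gap in the endpoint definition, subject to Appendix E and to the individualized course.

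**What to change.** - Reconcile 3.4, 3.5.1, 5.6 and Appendix E so that one rule governs escalation and withdrawal after 30 mg, and say whether it rests on AEC alone or on AEC and symptoms. Which clinical rule applies is for the investigators to decide.
- In 3.5.1, state the precedence of the limbs, so that a subject with no first-week drop who is later controlled on taper has one defined value.
- State that a subject not controlled at 30 mg and not escalated is not scored as controlled at 30 mg. For the Spearman test, rank that subject above those controlled at 30 mg. A rank supplies neither a number for the linear models (including the interim model in 6.4) nor a category for the cumulative logit model, so fix that value or category in advance and add a sensitivity analysis to it.
- Re-score past subjects from existing dose, count and symptom records, blinded to the eosinophil response rate (ERR), and report the result against any interim analysis already produced.

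The cost is protocol wording, a small amount of re-scoring and one added sensitivity analysis. No extra visits are needed.

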# 6. Analysis Plan

## 6.1. Description of the Analyses

The primary objective of this study is to develop a model to predict GC responsiveness (see section 2) using the percent change in the eosinophil count at 4 or 24 hours following steroid challenge (ie, ERR). GC responsiveness is defined as the dose required to control disease manifestations and eosinophilia. Since this response is necessarily subject to many factors including physician expert opinion, it is important that the PI and Accountable Physician be blinded to the predictor variables. In order not

to compromise patient care, the 24 hour post-challenge CBC with differential will be assessed by an independent physician ([name] or her designee) who will decide whether un-blinding is necessary for patient safety.

To allow for flexibility in building the predictive model, we will first try the class of linear models on the GC responsiveness and pick the best model in terms of a small sample adjusted Akaike Information Criterion(16). If the fit of that model is not good (for example, the errors look far from normal), then transformations on the GC responsiveness may be tried. If none of those models have good fit, then we will consider a cumulative logit model where we partition the GC responsiveness into 3 ordered categories: steroid responsive (<15 mg of prednisone or equivalent alternate corticosteroid daily), moderately responsive (requiring between 16-40 mg of prednisone or equivalent), or resistant (>41 mg of prednisone required daily with or without a response).

The primary objective of this study is exploratory, because we are looking for the best model for prediction and do not want to limit ourselves to 1 class of models. In order to protect ourselves from creating a model that appears to predict the response when in fact there is no real relationship between the predictors and the response, we will first test for a significant Spearman correlation between GC responsiveness and ERR to make sure that there is a significant effect. If there is a significant correlation, then we have some comfort that our final model is not just modeling noise. For our sample size justification (section 6.2), we assume that if we have a large enough sample size to show a significant correlation between GC responsiveness and 1 of the continuous predictive variables, then we would have a sample size large enough to explore these models. Because our objective is to find a reasonable model, and sample sizes are limited by availability of subjects, the sample size calculation is mostly to ensure that with such small sample sizes we would be able to detect moderate (i.e., correlations of about 0.5) effects.

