### **6.1.2. Addressing Study Objectives**

Although the primary objective is an exploratory model building, we do consider the simple null hypothesis that there is no correlation between % change in eosinophil count at 4 and 24 hours after challenge and GC response. Regardless of whether that test is significant or not, we will attempt to predict the GC response through the model building strategy described in the Section 6.1 on Description of the Analyses.

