## 6.2. Sample Size Justification

The sample size of this study is practically limited by the number of subjects available for study. Currently, about 30-35 new hypereosinophilic subjects per year are seen at the NIH and enrolled on protocol 94-I-0079, of which approximately 10% would meet inclusion criteria for this protocol. Consequently, we expect that we can enroll 30-40 subjects in this study over a 13-year period.

To show that this number of subjects is not unreasonably small, we calculate the sample size for a Spearman's correlation coefficient. If true correlation is 0.5 between a predictor variable (ERR at 4 or 24 hours) and the GC responsiveness (see Description of the Study, Section 3.1), the total number of subjects needed to show that the correlation is different from zero at the two-sided 0.05 level with 80% power is about 32 subjects. We calculated this by simulating 10,000 data sets of 32 bivariate random normal variables with correlation 0.5 and seeing that the Spearman coefficient is significantly different from zero 79.5% of the time. This is similar to the usual sample size calculation for Pearson's correlation(17) or (18) that gives a sample size of 29 for the same situation.

Because the predictor and outcome variables are both continuous, if the true change in the dependent variables is 0.5 standard deviations per 1 standard deviation change in the independent variable, a clinically important measurement of association between response to a steroid challenge and final required dose of GC will be possible.

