## 6.3. Final Analysis Plan

### 1. Study Endpoints:

- Primary: GC responsiveness.
  - Definition: See primary endpoint for definition of GC responsiveness.
  - Validity and Reliability: This is a rare disease, and standard care for this disease is still being developed. There is no standard endpoint, and this endpoint has not been used before. One of the purposes of this study is to see if this endpoint can be reliably predicted. The endpoint has face validity because the dose that controls eosinophil concentration is useful for determining the extent of a subject's disease and their responsiveness to steroid therapy. We will first try and predict GC responsiveness as described in section "Description of the Analyses" (Section 6.1), but may also try to predict the categorization of the GC responsiveness into 3 ordered categories described in section "Description of the Analyses".
  - Predictor Variables: All predictor variables will be measured in the first 24 hours after initial dose, and will be blinded to the PI and Accountable Physician. These variables will be used to predict the GC responsiveness:

percent change in eosinophil count from baseline to 4 and 24 hours and steroid absorption.

- Secondary:
    - Classification of subjects by GC response for assessment of clinical factors associated with GC responsiveness (including HES variant, pattern of organ involvement and laboratory parameters)
  - Exploratory
    - Exploratory analyses of potential mechanisms and in vitro correlates of GC resistance, including impaired steroid absorption, cell surface markers on lymphocytes, intracellular and serum cytokine profiles.
2. Description of the Statistical Methods to Be Employed:
    - Spearman correlation of GC responsiveness and percent change in eosinophil from baseline to 4 and 24 hours, with confidence intervals and testing whether it is different from zero.
    - Model building as described in section “Description of the Analyses” (Section 6.1).
  3. Level of Significance to be Used: Two-sided 0.05
  4. Exploratory Analyses: See section 6.1 for primary objective. Similar model building strategies will be used for secondary endpoints and exploratory endpoints.

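### The final prediction model is chosen by a data-driven search, but the plan neither validates it nor names a measure of how well it predicts

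*Combined protocol and SAP*

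**What the plan says.** The primary objective (Section 2.1) is a model that predicts glucocorticoid (GC) responsiveness from a single-dose challenge. Section 6.3 lists three predictors: "percent change in eosinophil count from baseline to 4 and 24 hours and steroid absorption". ERR below is the percent change in eosinophil count.

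Section 6.1 describes the final search in three steps:

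- Among linear models, "pick the best model in terms of a small sample adjusted Akaike Information Criterion".
- If the fit is poor, for example because "the errors look far from normal), then transformations on the GC responsiveness may be tried".
- Should transformation not help either, the class of model may change: "If none of those models have good fit, then we will consider a cumulative logit model".

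The statistical methods in Section 6.3 are Spearman correlations with confidence intervals, and model building by reference to Section 6.1. The protection offered against a spurious model is the Spearman test of ERR: "If there is a significant correlation, then we have some comfort that our final model is not just modeling noise". Section 6.1.2 states its null hypothesis as "there is no correlation between % change in eosinophil count at 4 and 24 hours after challenge and GC response", and then adds: "Regardless of whether that test is significant or not, we will attempt to predict the GC response through the model building strategy".

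Section 6.4 treats the interim model differently. It allows three polynomials in log ERR at 4 hours, warns that trying many models can overfit, and estimates R squared by leave-one-out cross-validation with the selection step repeated in each fold.

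**The concern.** Small-sample AIC (AICc) ranks candidates. It does not say how well the winner predicts, and it does not cover the later steps, which are triggered by judgement. If accuracy is read off the subjects who chose the model, it will be too favourable. The three-model interim search is protected against this, and the wider, open-ended final search is not.

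Prediction is the main product of the study. Section 1.1 foresees using a failed challenge to identify patients in whom a steroid trial is not worth making, and Section 6.3 gives reliable prediction of the endpoint as one purpose of the study. An accuracy figure that is too high, or none at all, leaves that question unanswered.

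**Working it through.** **Inputs from the plan.** Sample size: "we expect that we can enroll 30-40 subjects in this study" (Section 6.2). Planned correlation 0.5, two-sided 0.05 (Sections 6.2, 6.3). Three predictors (Section 6.3).

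**The plan's own figure.** Section 6.2 gives 79.5% power for Spearman at n = 32 and correlation 0.5. Simulating 40,000 bivariate normal sets gives 80.1%, so it reproduces. It sizes a test of association and says nothing about predictive accuracy.

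**Assumptions.** The plan gives no candidate list. Assumed here: normal variables, the 8 linear subsets of the three predictors including intercept-only, mutual predictor correlation 0 to 0.8 in the no-association case, n = 30 to 40.

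**Formulas.** With k counting the coefficients plus the error variance:

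- AICc = n ln(RSS/n) + 2k + 2k(k+1)/(n−k−1)
- apparent R² = 1 − RSS/SST
- leave-one-out R² = 1 − Σ(yᵢ − ŷ₍₋ᵢ₎)²/SST, with the whole search rerun without subject i
- true R²: the same ratio for the fitted model in new subjects

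**Hand check, n = 36, no association.** The penalty is 4 + 12/33 = 4.36 for intercept-only (k = 2) and 6 + 24/32 = 6.75 for one predictor (k = 3), a difference of 2.39. One predictor wins if R² > 1 − exp(−2.39/36) = 0.064, that is |r| > 0.253. Then t = 0.253 × √34/√(1 − 0.064) = 1.53 on 34 degrees of freedom, p = 0.136. AICc thus admits a single useless predictor about 13.6% of the time. With three independent ones the chance that at least one enters is 1 − 0.864³ = 0.355.

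**Simulation, no association (10,000 sets per cell).**

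| Quantity | n = 36, correlation 0.5 | All cells |
|---|---|---|
| Non-null model picked | 33.5% | 29-37% |
| Apparent R² > 0.10 | 19.7% | 17-26% |
| Apparent R² > 0.20 | 4.2% | 3-8.5% (separate run, 3,000 sets per cell) |
| Leave-one-out R² > 0.10 | 1.9% | 1-3% |

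When a non-null model is picked, its median apparent R² is 0.09 to 0.16 and its median true R² is −0.13 to −0.19, so it predicts worse than the mean dose. Both ERR Spearman tests are non-significant in 90-92% of these sets, and a non-null model is still picked in 23-30% of those. Adding skewed doses and a log-transformation step barely changes the picture: 30-37% non-null, 16-27% with apparent R² > 0.10, 1-3% with leave-one-out R² > 0.10.

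**Simulation, true correlation 0.5 for 4-hour ERR only (population R² 0.25; 6,000 sets per cell).** Correlation between the two ERRs 0.5, and of each with absorption 0.3:

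| n | Mean apparent R² | Mean true R² | Mean leave-one-out R² | Apparent − true |
|---|---|---|---|---|
| 32 | 0.283 | 0.155 | 0.109 | 0.128 |
| 40 | 0.280 | 0.184 | 0.148 | 0.096 |

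Over all cells the overstatement is 0.10-0.14. A wider set of 18 candidates (polynomials and one interaction added; 100 sets per cell) gave mean apparent against median true R² of 0.32 against 0.16 at n = 32 and 0.30 against 0.20 at n = 40.

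**Do other parts of the plan close the gap?** The Spearman test does not gate the modelling, does not cover absorption, and measures association only. The check on later subjects in Section 6.4 concerns the interim model, applies only if its cross-validated R squared is large (no threshold given), expects fewer than 15 subjects, and by the plan's own account can detect only extreme departures.

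**The case against.** The best case for the plan has four parts.

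- **No inflated figure is promised.** The plan never says it will report apparent R squared for the final model; it commits to Spearman estimates with intervals. This is right. The defect in the text is an unnamed measure, and overstatement is the risk that follows from it.
- **A null search seldom looks like the planned effect.** Apparent R squared above 0.20 occurs in only about 4% of null sets at n = 36. This stands. When the effect is real, most of the gap arises because a model fitted to few subjects predicts worse than the true model: at n = 32, 0.25 − 0.155 = 0.095 of the 0.128. No validation method removes that loss, but cross-validation shows it, and a user of the model will experience it.
- **The plan has some protection.** It calls the objective exploratory, penalises complexity, adds Spearman as a check against noise, and obtains an honest cross-validated R squared for a 4-hour model from about two thirds of the projected subjects. That estimate does not carry over to a model reselected on everyone from more predictors. An exploratory aim relaxes error control, not the need for an honest accuracy estimate.
- **The size depends on assumptions.** It does, and the cumulative logit step was not simulated. The gap in the text does not depend on them.

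**Conclusion.** The concern holds. On the text alone, the final model has no internal validation and no stated accuracy measure, while the narrower interim search has both. How much in-sample fit would mislead is illustrative and rests on the assumed candidate set and correlations: about 0.10-0.14 in R squared if the planned correlation of 0.5 is real, and a spurious non-null model in roughly a third of data sets if there is no association. This should be corrected before the final analysis. It does not threaten the Spearman test, whose stated power reproduces.

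**What to change.** 1. In Section 6.1, list the final candidate models, including intercept-only, and write the transformation step and the switch to cumulative logit as rules a program can rerun.
2. Repeat the whole path in each leave-one-out fold, as Section 6.4 does for the interim model, and score all folds on one scale stated in advance, so that folds choosing different model classes can be combined.
3. In Section 6.3, name cross-validated R squared (or a cross-validated ordinal measure if the cumulative logit model is chosen) as the main measure of prediction, with a statement of its uncertainty. One option is to compare it with its distribution when doses are permuted and the whole path is rerun.
4. In Section 6.1.2, add that if neither ERR Spearman test is significant, the report says an association of ERR with GC responsiveness was not shown. Keep this to ERR: if only absorption correlates 0.5 with dose, both ERR tests are non-significant and absorption is selected in 74-87% of sets, with a median true R squared of 0.21-0.22.

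**Cost.** SAP wording, statistician time and some computing; no new subjects or visits. The reported fit will be less favourable, and it will be imprecise: at a true correlation of 0.5 the 10th-90th percentile range of leave-one-out R squared is −0.15 to 0.35 at n = 32 and −0.06 to 0.34 at n = 40, averaging 0.03-0.05 below the true value. A simple bootstrap of held-out errors should not supply the interval, since a nominal 95% interval covers 78-81%. The permutation comparison detects a true 0.5 in 67% of sets at n = 32 and 76% at n = 40, so it supplements the Spearman test and does not replace it.
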